A variety of approaches will be used to retain patients. Based on our experience, we understand the importance of creating a pleasant clinic environment and friendly and welcoming staff presence. We are also very clear from the initial screening session onward about what we expect from patients and what they can expect from us, as keeping patients well informed enhances adherence to the intervention and test schedules. Further, we will provide small gifts to patients including hats, umbrellas, coffee cups, etc., with the study logo, which has improved retention in our previous studies. Finally, a total of \$375/patient is budgeted for incentives related to the provision of outcome measures. All patients will be paid at the completion of each assessment visit (\$75 at each of baseline, 6, 12, 18 and 24 months).

9. Randomization and Blinding

Randomization

This is a cluster-randomized trial, and enrolled patients at a given clinic will receive the intervention assigned to their clinic. A pool of 18 clinics will be randomized to either 1) usual care or 2) intervention, after stratification by health system. Stratification by health system is necessary to ensure adequate local staffing of clinics assigned to the intervention arm, representation from all regions of the state and types of health systems in both arms of the trial.

Blinding

Given that this trial is randomized at the clinic level and the interventions are very distinct, PROPEL patients will know their group assignment, as will clinic staff and health educators that are involved in delivering the intervention. However, every effort will be made to blind staff involved in data collection to the clinic randomization, and all intervention staff will be blinded to the patients' official study measurements.

10. Intervention Methods

Overview of Intervention Arms

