The focus of the PCORI Funding Announcement under which this study was funded is on obesity reduction in adults therefore the patients in this study are mainly adults (20 - 75 y of age). The treatment of childhood obesity is beyond the scope of this intervention.

15. Power and Sample Size

The sample size calculations for PROPEL were based on LOSS, a pragmatic clinical trial conducted by Pennington Biomedical in eight primary care clinics across the state of Louisiana comparing intensive medical intervention for obesity versus usual care.⁴ According to the 2013 *AHA/ACC/TOS Obesity Guidelines*, as little as 3-5% weight loss is likely to result in clinically meaningful health outcomes.²⁹ The calculations assume that the study will be powered to detect a mean weight loss in the intervention arm of 3.5% at 2 y, relative to usual care, in race- and sex-specific subgroups. We are targeting a mean weight loss of >5% which we anticipate to be 3.5% more than usual care. Both the total and relative weight loss meet currently accepted levels of clinical significance.

Power calculations used a nominal 0.05 significance level with a two-tailed test with minimal power of 80%. Based on the LOSS study, the standard deviation for weight change for patients nested within clinics was 8.4%. For the subgroup analysis, a net sample size of 184 patients (92/arm) is sufficient for detecting a 3.5% weight loss with 80% power when randomization is performed at the patient level. After accounting for the design effect, at least 134 patients per arm are required to realize 80% power in a trial randomized at the clinic level. A previous study in primary care (PROACTIVE) had 20% attrition over 24 months. However, given the challenges of working with a clinic population across an entire state, we have allowed for a conservative estimate of 30% attrition for this trial. Thus, allowing for 30% attrition, at least 192 patients per arm are needed with a total (2 arms) enrollment of at least 384 patients per subgroup analyses.

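### The 80% subgroup power at 134 per arm follows from a design effect alone; on the plan's own figures, with at most 16 clinic degrees of freedom, it is about 76%

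*Combined protocol and SAP*

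**What the plan says.** Section 15 (Power and Sample Size) describes a study "powered to detect a mean weight loss in the intervention arm of 3.5% at 2 y, relative to usual care, in race- and sex-specific subgroups". On the error rates it says "Power calculations used a nominal 0.05 significance level with a two-tailed test with minimal power of 80" percent. On variability it says that "the standard deviation for weight change for patients nested within clinics was 8.4" percent. It then takes two steps:

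- Patient-level randomisation: "a net sample size of 184 patients (92/arm) is sufficient for detecting a 3.5% weight loss with 80% power".
- Clinic-level randomisation, with the design effect applied: "at least 134 patients per arm are required to realize 80% power in a trial randomized at the clinic level".

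The Technical Abstract (Section 2) gives the same two steps. The sample-size item in the Data and Safety Monitoring Plan (Section 14, V.E) gives the same 134 per arm at 80%, but starts from 126 per arm at 90% power. That is a separate inconsistency and does not affect this point.

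The 134 is raised to 192 per arm for 30% attrition, giving 384 per subgroup and 768 in total. At 768, Sections 14 and 15 claim at least 97% power in the whole sample. Up to 850 are then to be enrolled, and the extra is assigned to higher attrition in Federally Qualified Health Centers.

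On the unit of randomisation, Section 9 says: "A pool of 18 clinics will be randomized to either 1) usual care or 2) intervention, after stratification by health system". Section 16 specifies a multi-level mixed model fitted by restricted maximum likelihood and names no denominator degrees-of-freedom method. No section gives an ICC, a design-effect value, a subgroup cluster size, or degrees of freedom based on the number of clinics.

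**The concern.** A design effect inflates the variance of the difference between arms. It does not change the distribution to which the test statistic is referred. When clinics are randomised, the between-arm difference is judged against variation between clinics, and 18 clinics in two arms leave 18 − 2 = 16 degrees of freedom for estimating that variation. Each extra health-system term that is fitted removes one more. The patient-level figure of 92 per arm assumes about 182.

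Carrying 80% across this step unchanged therefore gives the clinic-randomised design the power of a test with far more degrees of freedom. The calculation matters because it produced the 192, 384 and 768, and because the plan sets 80% as its minimum for race- and sex-specific comparisons.

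**Working it through.** **Inputs (Section 15 unless noted).** Difference d = 3.5 points; SD = 8.4; two-sided α = 0.05; 92 per arm (patient level); 134 per arm (clinic level); 30% attrition; 18 clinics, so 9 per arm (425 per arm / 47 per clinic ≈ 9); stratification by health system (Section 9), number of strata not given.

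**1. Reproduce the plan.**
- Noncentrality at 92 per arm: 3.5 / (8.4 × √(2/92)) = 2.83.
- With 2 × 92 − 2 = 182 df, power = 80.3%, which matches the stated 80%.
- Implied design effect: 134/92 = 1.457. Effective size at 134: 134/1.457 = 92 per arm.
- 134/0.7 = 191.4, so 192 per arm, as stated.

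**2. Same effective size, clinic-level df.** The noncentrality stays at 2.83. With 16 df the critical value is 2.120.

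| df | Power |
|---|---|
| 182 | 80.3% |
| 16 | 75.6% |
| 14 (assumed: two further stratum terms) | 74.8% |
| 12 (assumed: four) | 73.7% |

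A simulation of clinic-mean t-tests with 9 clinics per arm also gave 75.6% at 16 df.

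**3. What restores 80% at 16 df.**
- About 150 completers per arm, if the design effect stays at 1.457: effective size 150/1.457 = 103, power 80.1%.
- Or a difference of 3.7 points at 134 per arm: noncentrality 3.7 / (8.4 × √(2/92)) = 2.99, power 80.1%.

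**4. At 850 enrolled, 30% attrition, 50% subgroup.** 425 × 0.5 × 0.7 = 148.75 per arm.
- Fixed design effect 1.457: effective size 102.1, power 79.8%.
- Design effect growing with clinic size. The implied ICC is (1.457 − 1)/(134/9 − 1) = 0.033. At 148.75/9 = 16.5 per clinic the design effect is 1.51, the effective size 98.5 and the power 78.4%.

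**5. Sensitivity to the unstated ICC.** 134 per arm, 14.9 per clinic, 16 df, design effect = 1 + 13.9 × ICC:

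| Assumed ICC | Design effect | Power |
|---|---|---|
| 0.01 | 1.139 | 85.1% |
| 0.02 | 1.278 | 80.8% |
| 0.03 | 1.417 | 76.7% |
| 0.033 (implied) | 1.457 | 75.6% |
| 0.05 | 1.694 | 69.2% |

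**6. Total sample at 768.** 384 × 0.7 = 268.8 completers per arm, or 29.9 per clinic.
- Fixed 1.457: effective size 184.5, noncentrality 4.00. Power is 97.9% with patient-level df, consistent with the stated figure of at least 97%, and 96.3% with 16 df.
- Growing at ICC 0.033: design effect 1 + 28.9 × 0.033 = 1.95, effective size 137.9, noncentrality 3.46. Power is 90.1% with 16 df.

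**The case against.** The strongest reply is that the derivation of 134 is not shown, so it may already allow for the small number of clinics. A design effect of 1.306 with 16 df gives 80.0% at 134 per arm. Held fixed, it also gives 97.7% in the total sample, which fits the claim of at least 97% as well as 1.457 with patient-level df does (97.9%). The total-sample figure therefore cannot tell the two readings apart. Further, at the ICC of 0.033 that 1.457 implies for the subgroup, the total sample would reach only 93.3% even with a normal reference. If the design effect grows with clinic size, a 97% figure points to an ICC of about 0.02 or less, where 134 per arm gives 80.8% or more at 16 df. An ICC of 0.01 at the full clinic size of 47 gives 1 + 46 × 0.01 = 1.46 and 92 × 1.46 = 134.3. If that is the origin of the 134, it is conservative for a subgroup of about 15 per clinic.

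What stands of this: 76% is conditional on the implied design effect, and the range must be shown. A reader might infer that the true subgroup power is 76% and that the trial is underpowered. The documents do not support that, because without an ICC the true power could lie on either side of 80%. What does not stand is the defence of the 80% as written. The text names only a design effect, and 1.306 appears nowhere.

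Two lesser replies. Enrolling 850 nearly closes the gap, but the plan commits that margin to extra attrition. A large-sample critical value of 1.96 would keep about 80% nominal power, but with 16 df the simulated type I error is about 6.7%, above the stated 5%.

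**Conclusion.** The point holds in conditional form. On the plan's own 92 and 134 per arm, the clinic-randomised design has about 76% subgroup power with 16 df, against the 80% stated, and slightly less if stratum terms are fitted. This rests on the plain reading that the design effect is the only adjustment, on equal clinic sizes, and on 9 clinics per arm. It concerns the between-arm effect within a subgroup, which is what the plan powers, and not the intervention-by-subgroup interaction.

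The shortfall is modest: about 5 points at 134 per arm, and about 0 to 2 points at 850 enrolled with 30% attrition (78–80%). A reader might also infer that the whole-sample comparison is in doubt. It is not: on the same basis its power is about 96% with a fixed design effect of 1.46, and about 90% if the design effect grows at ICC 0.033. The defect is a stated power that the documented calculation does not deliver, together with missing inputs that would settle the matter.

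**What to change.** In the Technical Abstract, the sample-size item of Section 14 and Section 15:

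1. Recompute the subgroup power with a t reference on clinic-level degrees of freedom (18 − 2, less any fitted stratum terms), and state the ICC and the subgroup cluster size used.
2. If the implied design effect of 1.46 stands, restate subgroup power as about 76% at 134 per arm, or give about 3.7 points as the difference detectable with 80% power. Add that it is about 78–80% at 850 enrolled with 30% attrition and a 50% subgroup.
3. Unless an ICC is given and justified, show the range at 134 per arm with 16 df: about 85% at 0.01, 81% at 0.02 and 77% at 0.03.
4. Recompute the total-sample figure of at least 97% in Sections 14 and 15 on the same basis, saying whether the design effect is fixed (about 96% at 768) or grows with clinic size (about 90% at ICC 0.033).

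This costs a recalculation and some rewording. Enrolment and conduct need not change. The only downside is that the stated figures become slightly less favourable.

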Secondary Aim 2. Examine the effects of the intervention on system-level practices and patient satisfaction with care.

The second secondary aim will be accomplished using a similar strategy as the primary aim.

Secondary Aim 3. Test the heterogeneity of effects (HTE) across clinics and across subgroups of patients (men versus women, white versus African American, older versus younger adults).

Analyses of HTE is an important aspect of this study, as the identification of systematic differences in response to the intervention will be important for broad dissemination of our model, and for further tailoring the intervention to specific sub-groups. We currently have three confirmatory HTE analyses planned: 1) white versus African American, 2) men versus women, and 3) younger (20-44 y) versus middle-aged (45-64 y) versus older (65+ y) adults. Further, we have one planned exploratory HTE analysis, which is to explore clinic-level differences in response within the intervention and usual care groups and identify factors that explain the clinic-level heterogeneity.

Confirmatory HTE Analyses. Based on one-year results in patients in the Look AHEAD intervention, men lost more weight than women, older adults (65+ y) lost significantly more weight than younger adults, and white participants lost more weight than African Americans.⁸³ Thus, we hypothesize that men, white patients, and older patients will lose significantly more weight in the primary care setting than women, African Americans and younger patients, respectively.

Exploratory HTE Analysis. There is potential for heterogeneity in response across the clinics in this study. We plan to explore clinic-level variability in response and identify factors

associated with clinic-level variability. Potential factors that will be considered include clinic size, number of physicians, number of residents, percentage Medicaid/Medicare, percentage minority, and geo-spatial characteristics of the clinic location (population density, crime, etc.).

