Heterogeneity of treatment effect will be investigated in several subgroup analyses: men vs women, whites vs African Americans, ages 20-44 y vs 45-64 y vs ≥ 65 y. The intervention effect on weight loss will be investigated using a subgroup variable in mixed effects multilevel models analogous to the primary analysis with a focus on intervention-by-subgroup interactions coupled with illustrative graphics. Subsequent analyses will focus on elucidating underlying reasons for the subgroup differences and how these differences influence guidelines that may translate to the general population. Exploratory analyses using fixed and random effects models will determine treatment differences among clinics and estimate the variability associated with these differences.

Significant subgroup heterogeneity in outcome response (e.g., significant sex differences in effectiveness), supported by significance of the test for intervention-by-sex interaction, would lead to further investigation in search of the underlying reasons for the differential response. Previous studies provide evidence that responses to weight loss interventions vary by age, race and sex.⁸³ It is anticipated that these will be confirmed in this trial. Less is known about the influence of clinic-level variables on treatment response; thus, these analyses are considered exploratory.

Handling of Missing Data

Missing data are expected due to drop outs and missed visits. Weight loss is a subject-level variable and missing assessments would influence tests relative to treatment-by-time interactions. The primary analysis described above will employ restricted maximum likelihood using all data. No patients will be deleted from the analysis because of partial data. To assess the sensitivity of results, weight loss will be analyzed using: 1) all patients irrespective of missing data to perform analysis of variance using mixed effects multi-level models with repeated measures; 2) only patients who have completed all assessment visits and have no missing data, to perform analysis of variance employing mixed effects multi-level models with repeated measures; 3) all patients, irrespective of missing data, to conduct analyses using mixed effects multi-level time trend models with random coefficients to capture individual time trends (does not require complete data across time); and 4) multiple imputation.

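### Section 16 calls three subgroup interaction analyses confirmatory but gives no multiplicity rule, so the chance of at least one false significant interaction is up to about 14% if none of the differences exists

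*Combined protocol and SAP*

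**What the plan says.** Under Secondary Aim 3, Section 16 sets out the heterogeneity-of-effect (HTE) analyses: "We currently have three confirmatory HTE analyses planned: 1) white versus African American, 2) men versus women, and 3) younger (20-44 y) versus middle-aged (45-64" and 65 and over). It contrasts these with a fourth: "Further, we have one planned exploratory HTE analysis, which is to explore clinic-level differences in response". The hypotheses have a direction: "Thus, we hypothesize that men, white patients, and older patients will lose significantly more weight in the primary care setting than women, African Americans and" (the third comparison is with those in the lower age bands).

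The same section specifies the method as "mixed effects multilevel models analogous to the primary analysis with a focus on intervention-by-subgroup interactions coupled with illustrative graphics", applied to "men vs women, whites vs African Americans, ages 20-44 y vs 45-64 y vs ≥ 65 y". On what follows from a positive result, it takes sex as the example: heterogeneity "supported by significance of the test for intervention-by-sex interaction, would lead to further investigation in search of the underlying reasons for the differential response". Of the age, race and sex differences reported by earlier studies it says: "It is anticipated that these will be confirmed in this trial".

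The only significance level is in the sample-size text (Section 15, repeated in the Technical Abstract and in Section 14, item V.E): "Power calculations used a nominal 0.05 significance level with a two-tailed test with minimal power of 80" percent. No section divides that level, orders the three tests or sets a family-wise limit. Section 16 also leaves open whether age is one overall test or several pairwise contrasts, and at which visit the interactions are judged. The primary model it refers to covers months 6, 12, 18 and 24.

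**The concern.** An analysis labelled confirmatory, and set apart from one labelled exploratory, is normally expected to carry a stated error rate. Here three such analyses sit under one aim, share one label and serve one purpose, and each would have its own full-level test. One chance finding among the three is enough to start the follow-up that Section 16 describes.

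What is at stake is a false statement that benefit differs by race, sex or age. Section 16 says these results should inform wider dissemination, tailoring to subgroups, and how guidelines might carry over to the general population. It also says that the analysis plan is flexible and may be adapted, so a rule left unwritten could be settled after the results are seen.

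**Working it through.** **Inputs from the document.** Three confirmatory factors, with age in three bands (Section 16). Two-sided 0.05, 80% power, a 3.5-point difference, SD 8.4, 92 per arm before the design effect, 134 per arm after it, 30% attrition and up to 850 enrolled (Section 15).

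**Assumptions.** Each interaction is tested at 0.05, with one test per factor unless stated. Race and sex split 50/50. The document gives no age distribution.

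**1. The plan's own figure.** No family-wise rate is stated, so the figure to reproduce is the subgroup size:

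- n per arm = 2 × (1.960 + 0.842)² × 8.4² / 3.5² = 90.4, rounded up to 91. The t-test version gives 91.4, rounded up to 92, as stated.
- 134 / 0.70 = 191.4, rounded up to 192, as stated.

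The subgroup sizing therefore used an unadjusted 0.05. At 0.05/3 = 0.0167 the same formula gives 2 × (2.394 + 0.842)² × 5.76 = 120.6, or 121 per arm.

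**2. Chance of at least one false significant interaction, independent tests.**

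| Situation | Formula | Result |
|---|---|---|
| None of the three differences exists | 1 − 0.95³ | 14.26% |
| One is real | 1 − 0.95² | 9.75% |
| Two are real | 1 − 0.95 | 5% |
| None exists, hypothesized direction only | 1 − 0.975³ | 7.3% |

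The comparator for the last row is 2.5% for one test. That row treats age as a single directional contrast, because a 2-df test has no direction.

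**3. Dependence between the tests.** Whatever the dependence, the rate cannot exceed 3 × 0.05 = 15%. With three equally correlated normal statistics it is 13.6% at a correlation of 0.3, 12.5% at 0.5 and 9.8% at 0.8.

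**4. Simulation with no true heterogeneity.** This used 850 × 0.70 = 595 completers, an assumed 30/55/15% age split, no clinic effect and 15,000 runs. The single tests rejected in 4.7%, 4.9% and 5.1% of runs, and at least one rejected in 14.0%. A second simulation, with 18 clinics of 33 patients, a clinic-adjusted model, an assumed 35/50/15% age split and 4,000 runs, gave 14.2%.

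**5. Age by three unadjusted pairwise contrasts.** In the 595-patient simulation, at least one rejection among race, sex and the three age contrasts occurred in 20.1% of runs.

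**6. Power cost of adjustment.** With 595 completers and 50/50 splits, and ignoring clustering, the standard error of a two-level interaction is 4 × 8.4 / √595 = 1.38 points.

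| True interaction | Power at 0.05 | Power at 0.0167 |
|---|---|---|
| 3.5 points | Φ(2.54 − 1.96) = 72% | Φ(2.54 − 2.39) = 56% |
| 1.75 points | Φ(1.27 − 1.96) = about 25% | Φ(1.27 − 2.39) = 13% |

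**The case against.** The strongest reply is that the document uses confirmatory to mean replication. Section 16 bases each hypothesis on an earlier trial's one-year results, and it calls the clinic-level analysis exploratory because less is known there. On that view these are three separate questions fixed in advance, each with its own 5% error, and no joint claim is made. Statisticians do differ on whether distinct secondary hypotheses form one family. This explains the label, but it does not supply an error rate for a set of analyses that the plan itself groups and sets against an exploratory one.

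Four stronger readings are tempting, and the document does not support them:

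- **That the trial has a 14% chance of confirming a difference that does not exist.** The 14% counts any significant interaction and needs all three nulls to hold, while Section 16 cites prior evidence against all three. In the hypothesized direction the figure is 7.3%. The 14% remains relevant because Section 16 would follow up a significant interaction without requiring a direction.
- **That the plan sets 0.05 for each interaction.** It speaks only of significance; the 0.05 belongs to the power calculations. Using it is an inference, though no other level is available.
- **That one false result would change care.** The stated consequence is further investigation. Tailoring and guidelines are named as aims, and no rule ties them to a single p-value.
- **That pairwise age testing gives 1 − 0.95⁵ = 22.6%.** Three contrasts among three groups are linearly dependent, so five independent tests cannot arise. About 20% is the right size.

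The objection that adjustment is costly also stands. Section 15 sizes the treatment effect within subgroups, so the interactions were never planned at 80% power.

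**Conclusion.** The concern holds in a limited form. Three analyses are called confirmatory and judged on significance, with no multiplicity control. The resulting chance of at least one false significant interaction is up to about 14%, and how far below that it lies depends on how many of the differences are real, on the correlation between the tests and on whether direction counts. It rises to about 20% if age is split into unadjusted pairwise contrasts. Judging the interactions at several visits could raise it further; that was not quantified.

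These figures rest on an inferred 0.05 per test, near-independence of the tests and, for the simulations, an assumed age split. Only Secondary Aim 3 is affected. The type I error of the primary between-arm comparison is unchanged. The point is worth correcting because it decides which subgroup statements the trial may call confirmed.

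**What to change.** Amend Section 16 in one of two ways.

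**(a) Keep the confirmatory label.** Test one interaction per factor at month 24: sex (1 df), race (1 df) and one overall age test (2 df). Control the three by Holm at two-sided 0.05, with successive thresholds of 0.0167, 0.025 and 0.05. Examine pairwise age contrasts only if the overall age test passes. Use the word confirmed only for interactions that pass, and report the others as estimates with confidence intervals.

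**(b) Relabel the three analyses as exploratory.** Report interaction estimates with confidence intervals and make no confirmatory claim.

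Either change takes a few sentences and no new data. Option (a) lowers power per interaction, by the amounts in step 6 of the working at the first Holm step. Option (b) costs no power but gives up the confirmatory claim. Given that the interactions were not sized, (b) is a reasonable choice if the sponsor finds the loss under (a) too large.
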